9.3.2 Sample Size/Accrual Rate

The first primary objective of this study is to evaluate the histological evidence of anti-tumor activity of hu14.18-IL2 by comparing pathological endpoints between the two groups after dichotomizing the evaluation of apoptosis, necrosis and cellular infiltrate into *positive* (i.e., the microscopic evaluation is classified as “low”, “medium”, or “high”) or *negative* (i.e., the evaluation is classified as “none”) using Fisher’s exact test. With eight subjects per group, a difference of 70% in the proportions of subjects classified as *positive* for necrosis, apoptosis, or cellular infiltrate between the two study arms will be detected with at least 82% power at a two-sided significance level of 0.1. A difference of 60% will be detected with at least 64%. Smaller differences are unlikely to be detected as statistically significant. The sample size chosen is sufficient to provide accuracy in the estimated rate of subjects classified as *positive*. Specifically, with eight subjects per group, the standard error of the proportions of subjects classified as *positive* necrosis, apoptosis, or cellular infiltrate for each group will be at most 0.18.

The second primary objective of this study is to evaluate the time to recurrence (duration of remission) and overall survival relative to historical control data described in Section 1.3.3. This study is not designed to detect differences in time to recurrence or overall survival between the two study arms. Instead, time to recurrence and overall survival time of both arms combined will be compared to historical controls qualitatively. Time to recurrence and overall survival time will be summarized using point estimates of the median time to recurrence/overall survival time and associated 90% confidence intervals. Furthermore, the two-year recurrence free survival rate and the two-year survival rate will be reported along with the corresponding 90% confidence intervals. The following table gives (two-sided) Wilson’s score 90% confidence intervals for the two-year survival/two-year recurrent-free survival rates, assuming a total sample size of 16 subjects.

Table 9: Ninety percent confidence bounds for two-year survival/two-year recurrent-free survival rates

Observed number of subjects alive/recurrent-free after 24 months	Proportions of subjects alive/recurrent-free after 24 months	Lower 90% confidence limit	Upper 90% confidence limit
2	0.12	0.04	0.32
4	0.25	0.12	0.45
6	0.38	0.21	0.58
8	0.50	0.31	0.69
10	0.62	0.42	0.79
12	0.75	0.55	0.88
14	0.88	0.68	0.96

Therefore, with a sample size of 16 subjects, the 90% confidence interval for the two-year survival/two-year recurrent-free survival rate will be no wider than 38%.

Secondary endpoints of this pilot study include adverse events, immunological parameters, density & phenotype of cellular infiltrate and expression of GD2 target antigen, and IFN- γ expression. Assuming a total sample size of 16, the probability of observing at least one incidence of Grade ≥ 3 toxicity is 81%, if the true toxicity rate is 10%. Analogously, the probability of observing at least one incidence of Grade ≥ 3 toxicity is 93%, if the true toxicity rate is 15%. Immunological parameters will be measured on a continuous scale. Assuming a sample size of eight subjects per

study arm, a difference of 1.5 standard deviation units in magnitude will be detected with 80% power at a two-sided significance level of 0.05 (based on a two-sample t-test). A difference of only 1.25 standard deviation units will be detected with 63%. Smaller differences are unlikely to be detected as statistically significant.

In order to account for “unevaluable” subjects and drop-outs (e.g., patients without an evaluation following course 2 of IC treatment), we will accrue up to 20 eligible subjects (10 per arm) in total. Based on our past experience with advance melanoma subjects treated at UWCCC, we expect to accrue 20 eligible subjects within 24 months. The minimum follow-up period will be 12 months after the last subject has entered the study.

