9.2 Definition of Study Endpoints

9.2.1 Primary Endpoints

Pathology evaluations of necrosis, apoptosis, and cellular infiltrate:

Pathology evaluations of necrosis, apoptosis, and cellular infiltrate will be performed on a standard scale with 4 categories: "0" (none), "+" (low), "++" (medium), or "+++" (high). These evaluations will be performed independently by two pathologists in a blinded fashion. In the case of a disagreement, the tumor tissues will be evaluated by a third pathologist.

Time to recurrence (duration of remission):

For a given subject, time to recurrence will be defined as the number of days from the day of evaluation following course 2 of IC treatment to the day the subject experiences an event of recurrence or death, whichever comes first. All subjects on this study have disease deemed to be completely resectable, and all subjects are expected to be going into complete remission following surgical resection. Uniformity of follow up time is best provided by clarifying the time after “study evaluability” that recurrence is first identified (and confirmed whenever possible). As such, the time point of “study evaluability” will be designated the day of evaluation following course 2 of IC treatment, when CR is first demonstrated clinically and radiologically. Subjects in Group A and Group B will each have spent equivalent time since study entry in getting to this point: each will have had their surgical resection and their first 2 courses of IC treatment. The only difference is that surgery is before course 1 for Group A and after it for Group B.

If a subject has not experienced an event of recurrence (or death) at the time of analysis, then the subject’s data will be censored at the date of the last available evaluation

Overall survival:

Overall survival will be defined as the number of days from the randomization to the date of the subject’s death. If a subject is alive at the time of analysis, then the subject’s data will be censored at the date of the last available evaluation

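### The stated minimum powers of 82% and 64% are not what Fisher's exact test delivers (80.0% and 61.4%), and the 38% interval width omits its condition of complete 24-month status

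*Combined protocol and SAP*

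**What the plan says.** For the first primary objective, Section 9.3.2 dichotomises each pathology score into positive or negative and compares the groups by Fisher's exact test, eight subjects per group. Its statement on a difference of 70% reads: "detected with at least 82% power at a two-sided significance level of 0.1. A difference of 60% will be detected with at least 64" per cent. The positive rate in either group is not stated. The section adds that the standard error of the proportion positive for necrosis, apoptosis or "cellular infiltrate for each group will be at most 0.18".

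For the second primary objective, Table 9 gives Wilson 90% intervals for the two-year rates, "assuming a total sample size of 16 subjects". The section concludes that "the 90% confidence interval for the two-year survival/two-year recurrent-free survival rate will be no wider than 38" per cent.

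On size and timing it says "we will accrue up to 20 eligible subjects (10 per arm) in total" and "we expect to accrue 20 eligible subjects within 24 months", and then: "The minimum follow-up period will be 12 months after the last subject has entered the study". Under Section 9.2.1, subjects without an event are "censored at the date of the last available evaluation".

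**The concern.** A power quoted as a minimum should hold whatever the underlying positive rate, because only the difference is specified. With eight per group Fisher's test is coarse and its power depends strongly on that rate, so such a claim has to be checked at the worst case.

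The 38% limit is worded as something the trial will achieve. It treats all 16 subjects as having known status at 24 months, yet the guaranteed follow-up for the last subject entered is half of that. A reader could therefore expect a precision that an analysis at the minimum follow-up need not reach.

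At stake is the accuracy of the design figures behind the two primary objectives, not the choice of test or the number of subjects.

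**Working it through.** **Power: inputs (Section 9.3.2).** Fisher's exact test, 8 v 8, two-sided 0.10, differences of 0.70 and 0.60. The lower-arm positive rate p is not given, so it may lie in 0–0.30 for the first difference and 0–0.40 for the second.

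**Rejection region.** In each pair below, the first outcome rejects at 0.10 and the second is the nearest that does not:

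| Reject (p-value) | Do not reject (p-value) |
|---|---|
| 0 v 4 (0.077) | 0 v 3 (0.200) |
| 1 v 6 (0.041) | 1 v 5 (0.119) |
| 2 v 7 (0.041) | 2 v 6 (0.132) |
| 3 v 8 (0.026) | 3 v 7 (0.119) |
| 4 v 8 (0.077) | 5 v 8 (0.200) |

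The test therefore rejects for 0 v ≥4, 1 v ≥6, 2 v ≥7, 3 v 8 and 4 v 8 positives, in either direction.

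**Exact power.** Power(p, d) = Σₓ P(X = x | 8, p) · P(Y in the rejection set for x | 8, p + d). By lower-arm count x = 0, 1, 2, 3, 4 (further terms are negligible):

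- 15% v 85%: 0.27171 + 0.34422 + 0.15615 + 0.02285 + 0.00504 = **0.79997**
- 20% v 80%: 0.16603 + 0.26740 + 0.14777 + 0.02463 + 0.00770 = **0.61353**

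Across p (symmetric about the midpoint of each range):

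| Lower-arm rate | 70-point difference | 60-point difference |
|---|---|---|
| 0% | 94.2% | 82.6% |
| 5% | 85.4% | 72.1% |
| 10% | 81.2% | 65.7% |
| 15% | 80.0% (minimum) | 62.4% |
| 20% | 81.2% | 61.4% (minimum) |

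On a grid of 0.0001, power is below 82% for p from 8.66% to 21.34%, which is 12.68/30 = 42% of the possible range. It is below 64% for p from 12.04% to 27.96%, which is 15.92/40 = 40%. These are shares of the range only; the documents do not say how likely such rates are.

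**Can the plan's figures be reproduced?** Not as minima of the named test. Minima for the 70- and 60-point differences under other readings are:

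- doubled one-tail p, or one-sided 0.05: 80.0% and 61.4%
- two-sided 0.05: 79.0% and 59.4%
- mid-p, uncorrected chi-square, or one-sided 0.10: 92.2% and 80.1%
- ten per group: 93.3% and 80.5%

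The closest match is a continuity-corrected normal approximation at a 10% lower-arm rate (82.6% and 64.5%). That is neither Fisher's test nor a minimum, and no 10% rate appears in the plan.

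**Standard error.** √(0.25/8) = 0.177, so the limit of 0.18 is right.

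**Interval width: reproducing the plan.** At an observed proportion of one half, the Wilson 90% width is z/√(n + z²) with z = 1.645. For n = 16 this is 1.645/√18.706 = 0.3803. The rows of Table 9 agree, so 38% is correct for 16 known statuses.

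**What the follow-up guarantees.** The last subject entered is assured 12 months from entry. Time to recurrence starts later, at the evaluation after course 2. Using the group labels of Section 5.2 and counting treatment or surgery from the day of entry:

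- Group A at the earliest: course 2 on day 29, evaluated on its day 8, so day 36 (1.2 months).
- Group B at the latest on schedule: 28 days of surgical recovery + 35 to course 2 + 35 to the evaluation = 98 days (3.2 months).

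That leaves 12 − 3.2 to 12 − 1.2, or about 9 to 11 months from the recurrence time zero. Section 9.4.4 names Kaplan-Meier only for the plots, so how censored subjects enter the two-year interval is not stated.

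**Width when some statuses are unknown.** If only subjects with known 24-month status counted, the largest Wilson width would be:

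| Known | 16 | 15 | 14 | 13 | 12 |
|---|---|---|---|---|---|
| Width | 0.380 | 0.390 | 0.402 | 0.414 | 0.429 |

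If all 20 accrued subjects counted, up to four unknown would still leave 16 known and a width within 0.380.

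**Illustration only.** A simulation used assumptions that are not in the plan: analysis on the first permitted day (month 36), uniform accrual, exponential times, and a Wilson interval with an effective sample size from Greenwood's variance. With two-year rates of 33–50%, mean widths were 0.38–0.40 for overall survival from randomisation with 16 subjects, 0.35–0.37 with 20, and 0.38–0.42 for time to recurrence with 16. The 33% follows from the 15-month median survival in Section 1.5.3; the 50% is assumed. At 12.5%, which follows from the 8-month disease-free median there, the limit was exceeded in only 1–11% of trials, although 12–23% of trials had no 24-month estimate. Neither point depends on these results.

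**The case against.** The shortfalls are 2.0 and 2.6 points in a pilot of 16 subjects whose analysis is mainly descriptive, and no decision turns on 80% rather than 82%. The stated figures hold or are exceeded over more than half of the possible rates, and power is well above them when untreated tumours are rarely positive. All of this is true and limits the importance of the point, but it does not make the stated minima correct. Even at a 10% lower-arm rate, the exact power for a 70-point difference is 81.2%.

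It can also be said that the underlying fault is the missing positive rate, and that 79.997% is itself marginally below 80%. Both are fair: 80% is a rounded figure, and stating the assumed rate is an acceptable alternative.

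On the interval, Table 9 is plainly a planning calculation on 16 subjects counted at 24 months, and 12 months is a minimum rather than a scheduled analysis date. Follow-up continues until death, loss or withdrawal (Sections 5.5.1 and 5.5.2), with evaluations to month 24 and beyond (Section 6.3). Complete status is therefore attainable. What stands is that nothing ties the two-year analysis to it, while the conclusion is worded as a certainty. The simulated excesses are mostly small and rest on assumptions, so they should carry little weight.

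**Conclusion.** The concern holds. The minimum exact power is 80.0% and 61.4%, against the stated 82% and 64%. This follows by enumeration from the plan's own inputs, and the only interpretation needed is that a stated minimum covers all possible positive rates.

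The 38% width is right for 16 known statuses but is not guaranteed by the 12-month minimum follow-up with censoring. How far it would be exceeded depends on when the analysis is done, how many subjects enter it and how censored subjects are handled. The limit would still be met if at least 16 statuses were known.

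Both are small errors of statement that should be corrected. Sample size, test and Table 9 are unaffected.

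**What to change.** 1. In Section 9.3.2, restate the power as at least 80% for a 70-point difference and at least 61% for a 60-point difference (rounded exact minima). Alternatively, state the assumed positive rate and give the exact Fisher power at that rate.
2. For the 38% limit, either say that it assumes known 24-month status for all 16 subjects, or report each two-year rate only once every subject has reached 24 months from that endpoint's time zero or has had an event.
3. Before applying item 2 to overall survival, settle its time zero: Section 6.5 starts it at study evaluability and Section 9.2.1 at randomisation.

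Item 1 and the first option in item 2 are wording only. Waiting for complete status would delay the two-year rates beyond the earliest permitted analysis by about 24 − 12 = 12 months for survival from randomisation. For recurrence, or for survival from evaluability, the delay is about 13 to 15 months (12 plus the lag of 1.2 to 3.2 months). The follow-up this needs is already planned.

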At the time of study entry, subjects will be randomized to Group A or B. Subjects in both groups will receive 3 cycles of immunocytokine (IC) therapy. Immunocytokine therapy will be given on days 1, 2, and 3 of each 28-day treatment course. Subjects randomized to Group A will undergo surgical resection of all sites of known disease following the first course of treatment. Subjects randomized to Group B will undergo surgical resection of all sites of known disease prior to the first course of treatment. This treatment schema allows for evaluation of the biological effects on the tumor of one cycle of Hu14.18-IL2 therapy.

SURGICAL RESECTION FOR GROUP A

(Course 1 of protocol therapy prior to surgery):

[figure not shown]
Subjects randomized to **Group A** will have complete surgical resection of all detectable melanoma following Course 1 of protocol therapy. Surgical resection will be scheduled for 7-14 days following the completion of the first course of treatment (i.e., days 10-17) in order to insure reversal of toxicities prior to the surgery. Once the subject has recovered from the surgery (2-4 weeks, depending upon the nature of the surgery), the subject will begin Course 2 of treatment. Initiation of course 2 will not be sooner than 4 weeks (29 days) after day 1 of the first course of study therapy. A total of 3 courses of protocol therapy are planned.

SURGICAL RESECTION FOR GROUP B

(Surgery prior to Course 1 of therapy):

Subjects randomized to **Group B** will have complete surgical resection of all detectable melanoma upon study entry, prior to Course 1 of protocol therapy. Once the subject has recovered from the surgery (2-4 weeks, depending upon the nature of surgery), the subject will begin Course 1 of hu14.18-IL2 treatment. A total of 3 courses of protocol therapy are planned.

A summary of the treatment groups and how they differ is shown:

Study agent administration:

TREATMENT COURSE ¹										
WEEK	1							2	3	4
DAY	1	2	3	4	5	6	7	8-14	15-21	22-28
Hu14.18-IL2 ²	X	X	X							

¹ All subjects will be scheduled to receive a total of 3 courses of treatment. Treatment will be stopped if it can not be tolerated or if there is recurrent disease.

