2.2 Secondary objectives

2.2.1 Evaluate adverse events associated with this experimental agent (3 courses of hu14.18-IL2 treatment for 3 consecutive days administered on an every 4-week basis), as well as the potential late adverse effects of this treatment as detected months or years following treatment for subjects remaining in remission following treatment.

2.2.2 Evaluate the immunologic activation induced *in vivo* by hu14.18-IL2, by evaluating standard clinical labs, and research lab evaluations of serum and PBMCs obtained by blood samplings.

2.2.3 Determine the induction of anti-idiotypic antibodies (anti-hu14.18) and antibody against the part of the compound where IL2 is linked to the Fc end of the IgG (anti Fc-IL2) from blood samples, Determine the expression of the GD2 target antigens, obtained from all subjects in this study.

2.2.4 Evaluate the density and phenotype of the cellular infiltrate, IC binding, chemokine expression, and cytokine expression in tumor specimens from all subjects receiving hu14.18-IL2 before their surgical resection (i.e., Group A), and comparing these results to these same values obtained for tumor samples obtained prior to administration of any protocol treatment (i.e., Group B).

2.2.5 For subjects in Group A with tumor that is readily accessible for biopsy, to obtain a cutaneous/subcutaneous biopsy of a single readily biopsiable lesion before starting protocol treatment in course 1, to allow histology from it to provide a “pretreatment control” for the histological analyses of the resected tumor that will be removed surgically from that same subject following course 1 of study therapy.

2.2.6 For subjects who have autologous tumor cells for functional assays, autologous tumor cell lines that are able to grow *in vitro*, or who are HLA-A2+, evaluate cryopreserved PBMC obtained before and after protocol treatment to evaluate for augmentation of T cell reactivity to autologous tumor or to known melanoma antigens (gp100).

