6.4 Time to recurrence following “study evaluability”

As all subjects on this study have disease deemed to be completely resectable, all subjects are expected to be going into complete remission following surgical resection. Uniformity of follow up time is best provided by clarifying the time after “study evaluability” that recurrence is first identified (and confirmed whenever possible). As such, the time point of “study evaluability” will be designated the day of evaluation following Course 2 of study treatment, when CR is first demonstrated clinically and radiologically. Subjects in all treatment groups will each have spent equivalent time since study entry in getting to this point: each will have had their surgical resection and their first 2 courses of protocol treatment. The only difference is that surgery is before Course 1 for Group B and after Course 1 for Group A.

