9.4.5 Secondary Endpoints

The number and severity of toxicity incidents will be analyzed descriptively in tabular format. Immunological parameters, i.e., lymphocyte counts, NK/ADCC, soluble IL2, anti-idiotypic antibodies, and anti Fc-IL2, will be summarized by standard descriptive statistics in terms of means, standard deviations, medians and ranges for each measurement time point (see Section 7.3) and group separately. Within each group, differences between pre-IC treatment values and post-IC treatment values will be evaluated by paired t-tests and/or non-parametric Wilcoxon test.

Comparisons of immunological parameters between the two study arms will be performed by two-sample t-tests. Furthermore, longitudinal data analyses of immunological parameters will be performed to incorporate the time effect. Specifically, linear and/or nonlinear mixed effect models with subject specific random effects and generalized estimating equations (GEE) models with identity link and exchangeable (working) correlation structures will be used to account for the correlation between repeated measurements of immunological parameters. Missing data may be imputed using regression type imputation techniques. For immunological parameters not conforming to the assumptions of parametric analysis, the non-parametric Wilcoxon Rank Sum test will be used for comparing the two study arms. The association between the various immunological parameters will be examined by computing Spearman's rank correlation coefficients and linear or nonlinear regression techniques. Immunological parameters will be correlated with clinical endpoints by fitting Cox regression models (for clinical endpoints overall survival & time to recurrence) and logistic regression analysis models (for clinical endpoints toxicity and histological evidence of anti-tumor activity). The data of all immunological parameters will be presented graphically where possible (boxplots, histograms, profile plots and scatterplots).

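### For the blood measures of immune activation, the only stated power belongs to a between-arm test of surgery timing; the pre/post change that addresses activation is tested in groups of eight with no stated power

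*Combined protocol and SAP*

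**What the plan says.** Objective 2.2.2 concerns immune activation caused by the drug, to be assessed "by evaluating standard clinical labs, and research lab evaluations of serum and PBMCs obtained by blood samplings".

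The design has no untreated arm for these blood measures. The Schema states: "Subjects in both groups will receive 3 cycles of immunocytokine (IC) therapy". Section 6.4 describes how the arms differ: "The only difference is that surgery is before Course 1 for Group B and after Course 1 for Group A". (Section 9 swaps the Group A and B labels relative to the Schema and section 6.4. This does not matter for a symmetric comparison.)

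Section 9.3.2 gives two power figures for immunological parameters, both for eight subjects per arm and "based on a two-sample t-test". The first is that "a difference of 1.5 standard deviation units in magnitude will be detected with 80% power at a two-sided significance level of 0.05"; the second is 63% at 1.25 SD.

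Section 9.4.5 plans three kinds of analysis for these parameters:

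- Between arms: "Comparisons of immunological parameters between the two study arms will be performed by two-sample t-tests".
- Pre/post: "Within each group, differences between pre-IC treatment values and post-IC treatment values will be evaluated by paired t-tests and/or non-parametric Wilcoxon test".
- Longitudinal: mixed-effects and GEE models that take time into account. The text does not say whether the arms share a common time effect or which contrast would show activation.

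Neither the pre/post tests nor the longitudinal models have a stated power or precision. Secondary tests are at 0.05 without multiplicity adjustment and are described as exploratory.

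**The concern.** A test can only answer the question posed by its null hypothesis. For blood parameters the between-arm null is that having surgery before or after Course 1 makes no difference. In effect, it asks whether having tumour in place during Course 1 changes the response. If the drug activates lymphocytes strongly and equally in both arms, that null is true and the test should not reject.

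Section 9.3.2 adds that differences below those quoted are unlikely to reach significance. A reader looking for the trial's sensitivity to activation finds only this statement, and it concerns a different contrast.

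The paired tests do ask about activation, but each uses half the subjects. Elsewhere in 9.3.2 the plan combines the arms when the arm is not the question: time to recurrence and survival are summarised over both arms, and the toxicity probabilities use 16 subjects. Blood activation fits the same reasoning but is not combined in the paired tests.

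**Working it through.** **Inputs.** Eight per arm and two-sided 0.05 (9.3.2); paired tests within each group (9.4.5); same drug and courses in both arms (Schema, 6.4). The documents give no size or SD for the pre/post change, so a range is shown. All powers are exact noncentral-t values. They assume roughly normal changes, with the same mean and SD in both arms.

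**1. The plan's own figures.** Two-sample t-test: df = 2×8 − 2 = 14, critical t = 2.145, noncentrality = d × √(8/2) = 2d.
- d = 1.5: noncentrality 3.0, power 79.7% (plan: 80%).
- d = 1.25: noncentrality 2.5, power 64.3% (plan: 63%).

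Both are reproduced to within two percentage points.

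**2. The same test when the drug works equally in both arms.** The noncentrality depends on the difference between the arm means. If both arms change by the same amount, it is 0 and the rejection rate is 5%, whatever the size of the activation. A simulation of 100,000 trials with equal changes of 0, 1 and 2 SD gave 5.0% each time. This restates the null hypothesis; it shows what the test is for, not a fault in it.

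**3. Pre/post change, per arm or combined.** Let d be the mean change divided by the SD of the change.
- Per arm: df = 7, critical t = 2.365, noncentrality = d√8.
- Both arms, adjusted for arm: df = 14, critical t = 2.145, noncentrality = d√16 = 4d.

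| d | Per arm, n = 8 | Both arms, n = 16 |
|---|---|---|
| 0.75 | 44.9% | 79.7% |
| 1.0 | 68.1% | 96.0% |
| 1.5 | 95.1% | >99% |

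The change detectable with 80% power is 1.16 SD per arm and 0.75 SD combined. To express this in between-subject SDs, multiply by √(2(1 − ρ)), where ρ is the pre/post correlation. The documents give no ρ. Assuming 0.3 to 0.7, the detectable change is 1.37 to 0.90 per arm and 0.89 to 0.58 combined.

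**4. Parameters not measured in everyone.** Sections 7.3.4 and 7.3.6 limit NK/ADCC and T-cell studies to selected subjects. With df = n − 2, the arm-adjusted power at d = 0.75 is 65% for n = 12 and 43% for n = 8. The 80% figure therefore cannot be stated for every parameter.

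**5. Which pre value.** Table 7A gives soluble IL2 receptor and anti-hu14.18-IL2 antibody a pre-infusion sample on day 1 of Course 1. It shows no separate sample then for NK/ADCC and T-cell studies, which rely on baseline. Footnote 1 lets baseline be drawn at any time from 3 weeks before randomization until just before treatment. In Group B, where surgery comes first, that sample may precede or follow the operation.

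**The case against.** The case on the other side is substantial.

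- Section 9.3.2 never links the 1.5 SD figure to objective 2.2.2, and section 1.5.4.6 bases the sample size on pilot experience and tumour-tissue comparisons. A reader might infer that the trial was sized on the wrong test for activation. The documents do not support that; the sentence only describes what eight per arm can detect.
- A reader might also infer that the plan has no way of detecting activation. It has paired tests and longitudinal models, and the latter could estimate a time effect over all subjects. What is missing is a named contrast and its power.
- The objective is secondary and exploratory, and section 9.4.1 puts descriptive statistics first. Section 1.3.5 reports marked lymphocyte activation in the Phase I trial, so large changes are plausible. At 1.5 SD the per-arm tests already have 95% power.
- The between-arm comparison is not idle. Tumour burden during treatment is part of the trial's rationale (1.5.3, 1.5.4.5).
- It is tempting to argue that separate per-arm tests will lead to a claim of activation in one arm only. With equal changes, exactly one test is significant in 43% of trials at 1.0 SD (2 × 0.681 × 0.319) but only 9% at 1.5 SD. More importantly, the plan includes a direct between-arm test, which is the proper guard against that reading. This argument should not be relied on.
- Combining arms averages over surgery timing, and for assays with only a loosely timed baseline it may mix surgical and drug effects differently by arm.

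These points limit the concern and shape the fix. They do not alter the fact that the only powered contrast for the blood parameters is not the one objective 2.2.2 asks about.

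**Conclusion.** The point stands as an inexpensive improvement to an exploratory analysis. For the blood parameters of objective 2.2.2, the stated power is correctly calculated but applies to surgery timing. The tests aimed at activation are split by arm and carry no stated power.

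The loss depends on an effect size that the documents do not give: about 35 percentage points at a change of 0.75 SD (45% against 80%), 28 at 1.0 SD (68% against 96%), and about 5 at 1.5 SD. These figures rest on equal mean changes in the two arms, a common SD of change, and all 16 subjects being measured.

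The point does not extend to the resected-tumour endpoints of objective 2.2.4. There, one arm has been treated at resection and the other has not, so the between-arm test is the right contrast.

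**What to change.** **Section 9.4.5.** For the blood parameters of objective 2.2.2, make the mean pre/post change over both arms, adjusted for arm, the main analysis. The pre-to-post contrast from the time term of the planned mixed model would serve equally well. Show the per-arm changes descriptively, and keep the between-arm test as a comparison of surgery timing.

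**Section 9.3.2.** Label the 1.5 SD and 1.25 SD figures as referring to surgery timing. Add the combined power, about 80% for a change of 0.75 SD of the change at two-sided 0.05, only for parameters measured in all 16 subjects. For NK/ADCC and T-cell assays, state power at the number actually sampled (for example about 65% at n = 12 and 43% at n = 8 for 0.75 SD).

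**Pre value.** Use the Course 1 day 1 pre-infusion sample where there is one (soluble IL2 receptor, antibodies). Where there is none, note that a Group B baseline may fall before or after surgery, and report the combined change next to the arm-specific changes.

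**Cost.** Wording and a restated power figure; no new subjects, samples or data. The downside is that the combined estimate averages over surgery timing, which is why the arm-specific changes should stay on display.
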